11.2.5. Additional Efficacy Analysis: Random Effects (Site Differences) Analyses

We will conduct analyses based on mixed models that assume random effects and their variancecovariance matrix structure, including models without random intercepts, and possibly random slopes, for hospital sites.

12.0. Interim Efficacy Analyses

At the discretion of the DSMB, a formal interim efficacy analysis will occur after 375 subjects reach 180 days of follow-up. These analyses will be based on approximate O'Brien-Fleming stopping boundaries for efficacy (defined below).

In the MISTIE III design, subjects will be randomized to MIS+rt-PA versus medical management using a covariate-adaptive design described previously. The trial will initially enroll ICH patients until either a maximum of 500 eligible patients is accrued or the trial is stopped early for efficacy or futility using group sequential boundaries described below.

Analyses will be conducted after 375 and 500 patients, respectively, have 180-day post-stroke measurements. Efficacy stopping boundaries will be based on the error-spending (also called alpha-spending) approach using the power family with exponent rho=3, which approximates the O'Brien-Fleming boundaries. The (one-sided) alpha allocated to the analysis (called the interim analysis) at 375 participants is defined to be alpha₁ = $0.025(375/500)^3 = 0.0105$. All remaining alpha, i.e., (0.025-alpha₁) is spent at the analysis with 500 participants (called the final analysis).

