2.3.2. Safety Monitoring and Recruitment Suspension Rules

Safety events above pre-specified thresholds will trigger a "suspend recruitment and review" by the DSMB to investigate the presumed cause and impact of these events. Such events are initially reviewed by DCC staff to determine if an event threshold has been reached at which time the study investigators and the DSMB will be notified. The thresholds triggering such a review are: 30-day mortality >60%, a MIS+rt-PA–related symptomatic bleeding rate >25% (during active treatment or during the 72 hours after treatment will be monitored), first-week operative death rate >10%, and a procedure-related infection rate >15% (over the initial 30 days). If any of these SAEs are attributable to the intervention (catheter insertion or manipulation, or rt-PA injection), the study will be suspended for a complete safety review.

Interim analyses for efficacy will occur after 375 subjects are enrolled and 180 days outcomes are available. These analyses will be based on O'Brien-Fleming stopping boundaries for efficacy and more aggressive (i.e., more likely to stop if there is no early signal of benefit) stopping boundaries for efficacy and safety analyses will be every six months or at other intervals as determined by the external DSMB.

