4.0. Sample Size Determination for the Primary Efficacy Analysis

The MISTIE phase 2 results, for all available data (non-randomized trial-standardized "pilot" and randomized participants), demonstrated an estimated absolute increase in the probability of achieving an mRS 0-3 of 13.0% [95% CI: (0.4% to 26.4%)] comparing MIS+rt-PA treatment versus medical management 180 days post-stroke.¹ For the intention-to-treat (ITT) analysis, when only randomized patients are considered (n=96), the estimate for the unadjusted treatment effect is 10.9% [95% CI: (-8.8% to 29.4%)], and 16.2% [95% CI: (0.3% to 32.3%)] after adjusting for baseline clinical characteristics. This range of estimates provides a strong motivation for conducting MISTIE III to confirm these clinically beneficial findings. The analogous unadjusted and adjusted effect sizes based on non-lobar ICH patients are very similar to these effect sizes. The second stage of MISTIE II provided evidence of increasing frequency of mRS scores in the 0-2 categories between 180 and 365 days with an unadjusted proportion of mRS 0-3 increasing to 14%. The sample size was selected based on 180-day outcomes in MISTIE II.

It was decided to change the primary outcome to be based on 365-day outcomes because of the lack of a plateau in good functional outcome at 180 days.

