11.0. Efficacy Analyses

11.1. Primary Efficacy Analysis: Dichotomized, Adjudicated mRS 0-3 vs. 4-6 at 365 Days Post Ictus

This primary analysis will produce an estimate and 95% confidence interval for the average treatment effect comparing assignment to MIS+rt-PA treatment (MISTIE) versus control (standard of care, i.e., medical management), using the ITT principle. Specifically, we will estimate the difference between the probability of an adjudicated mRS score of 3 or less at 365 days post-stroke comparing assignment to

treatment versus control; this difference is called the average treatment effect. Below is a description of the procedure for computing estimators of the average treatment effect. We also will test the null hypothesis of zero treatment effect at level 0.05.

To estimate the average treatment effect, we will use the targeted maximum likelihood estimator (TMLE) of van der Laan and Gruber.³ This estimator adjusts for baseline (i.e., pre-randomization) variables in order to improve precision. The baseline variables, denoted by the vector B, include the three variables used in the covariate-adaptive randomization as given in Section 6.0 (i.e., pre-randomization clot volume, age, and baseline severity of impairment as measured by GCS) as well as the following additional variables: IVH volume and location of ICH (indicator of lobar vs. deep). All baseline variables are treated as categorical and included as main terms in the models below.

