14.4. Proposed Interval Safety Monitoring

The DCC will generate periodic DSMB reports. (We assume the total number of subjects enrolled per six months in a single treatment group will be approximately 30; thus, eight semi-annual looks at the data will be suggested to the DSMB. As usual, though, periods for reporting will be discussed and finalized at the initial DSMB meeting.) Each report will provide cumulative summary statistics on enrollment; subject status in the study (e.g., number completed at 3-month, 6-month, 9-month, and 12month assessments); baseline characteristics; protocol violations; safety data, including AEs and SAEs by AE code, severity, and relatedness to the study medication; outcomes data (if coinciding with an interim analysis—also to be discussed and finalized at the initial DSMB meeting); and data management/quality information (e.g., timeliness and completeness of data entry by the clinical sites via the MISTIE III electronic data capture (EDC) system; number of gueries generated and resolved). Two reports will be generated: an open report with combined data from both treatment groups, and a closed report for the DSMB voting committee members with data provided by blinded treatment group (noted as A and B). The outline of these proposed DSMB reports will be included in the Manual of Operations and Procedures prepared by the CCC. In an interval as yet to be determined (monthly, guarterly, or semi-annually), the CCC will also generate a Safety Monitoring Report to be distributed to the DSMB. This report contains only enrollment, subject study status, safety, and data quality information. The trial's Executive Committee will also receive the Safety Monitoring Reports. The DSMB will have discretion to recommend stopping the trial early if safety concerns become substantial. Safety stopping rules for each of the primary safety outcomes will be developed and used to help the DSMB make its safety assessments.

Minimally Invasive Surgery Plus rt-PA for ICH Evacuation Phase 3

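### The primary endpoint moved to day 365, but the efficacy looks are still timed on 180-day data: the interim names no endpoint, and the final look comes before 365-day follow-up is complete

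*SAP*

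**What the plan says.** SAP 4.0 records the decision to "change the primary outcome to be based on 365-day outcomes because of the lack of a plateau in good functional outcome at 180 days". SAP 11.1 follows it and estimates "the difference between the probability of an adjudicated mRS score of 3 or less at 365 days post-stroke", comparing the two arms. In SAP 2.2 and 13.5, mRS 0-3 at day 180 becomes secondary analysis 5a.

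The sections on the looks use day 180. SAP 2.3.2: "Interim analyses for efficacy will occur after 375 subjects are enrolled and 180 days outcomes are available". SAP 12.0 says that, at the DSMB's discretion, "a formal interim efficacy analysis will occur after 375 subjects reach 180 days of follow-up", and then: "Analyses will be conducted after 375 and 500 patients, respectively, have 180-day post-stroke measurements". SAP 12.0 spends one-sided alpha of 0.025(375/500)^3 = 0.0105 at the first look and all the rest at the second, which it calls final. Neither section names the outcome that the interim tests, and neither asks for 365-day data before a look.

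Protocol 9.1.9 has the same 180-day trigger, but there day 180 was the primary time point.

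**The concern.** A stopping rule has to say which hypothesis is tested and how much information about it is in hand. SAP 12.0 leaves the first open and counts the second in 180-day measurements.

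If the interim is read as a test of 180-day mRS, which is the natural reading of SAP 2.3.2, a boundary crossing stops the trial on a secondary outcome. The alpha spent there does not belong to the 365-day null. If it is read as a test of 365-day mRS, some of the 375 have not yet had the visit, and the 375/500 fraction does not describe the information on the primary estimate. At the second look, a literal reading uses up the remaining alpha while recently enrolled patients are still in scheduled follow-up. The 11.1 estimator would have to treat them as censored.

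The choice must be made before any unblinded look, because afterwards it would depend on the data.

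**Working it through.** **Inputs.** Triggers, spending exponent 3 and total one-sided alpha 0.025: SAP 12.0. Accrual, "the total number of subjects enrolled per six months in a single treatment group will be approximately 30": SAP 14.4, so about 60 in total. Control rate 25%: protocol 9.1.9. Thirty-day mortality of 10% and 15% in MISTIE II: protocol 2.2.

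**1. The plan's own figure.** 0.025 × (375/500)^3 = 0.010547, which reproduces 0.0105. The interim boundary is z = 2.306. With correlation √0.75 between the looks, the final boundary is z = 2.022. The arithmetic is sound; the question is which day's data the fraction counts.

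**2. Patients not yet at day 365.** The gap between the visits is 365 − 180 = 185 days. At 60 per 182.5 days, 60 × 185/182.5 ≈ 61 patients lie between them.

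| Look | Have reached day 180 | Have reached day 365 | Not yet at day 365 |
|---|---|---|---|
| Interim | 375 | about 314 | about 61 (16% of 375) |
| Final | 500 | about 439 | about 61 (12% of 500) |

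If accrual were 40 to 120 per six months (an assumed range), 334 to 253 would have reached day 365 at the interim, and 41 to 122 would not have done so at the final look.

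These counts are upper bounds on unknown outcomes, because a patient who has died has mRS 6. Removing only 30-day deaths at 10% to 15% leaves about 51 to 54 of 60. That is 10% to 11% of 500, or about 14% of 375.

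**3. If the interim tests 180-day mRS.** With 187.5 per arm and a control rate of 25%:
- 11-point effect: SE = √[(0.25×0.75 + 0.36×0.64)/187.5] = 0.0472. The expected z is 0.11/0.0472 = 2.33, and P(z > 2.306) ≈ 51%.
- 13-point effect: SE = 0.0475, expected z = 2.74, probability ≈ 67%.

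These chances of crossing depend only on the 180-day effect, whatever the 365-day effect is.

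**4. If both looks test 365-day mRS.** Counting only patients who have reached day 365, the interim fraction is about 314/500 = 0.63. This is a floor (see the objection). Keep the spend of 0.0105 (z = 2.306) and solve for the final boundary that gives 0.025 in total, with correlation √0.63: final z ≈ 2.05. If 2.022 is used instead, total one-sided error is about 0.0264.

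**The case against.** The strongest defence is that SAP 12.0 sets a time for the looks, not an endpoint. SAP 2.1, 2.2 and 11.1 all fix the primary test on 365-day mRS, and protocol section 8 follows all subjects to day 365. That stands for the final test. A reader might infer that the final analysis would be run on 180-day mRS; the documents do not support this. What remains is that its trigger precedes complete 365-day data. For the interim the defence is weaker, because SAP 2.3.2 ties it to 180-day outcomes and no text ties it to day 365.

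Three other inferences are tempting and do not hold.
- *Patients with only 180-day data carry no information on the primary.* The 11.1 estimator predicts the 365-day outcome from 180-day mRS, arm and baseline variables, so they contribute. If only the 375 are analysed, the interim fraction lies between about 0.63 and 0.75.
- *The interim alpha should be about 0.006 instead of 0.0105.* Applying the exponent-3 rule to 0.63 does give about that, but 0.0105 is a legitimate pre-specified spend. It still controls 0.025 if the final boundary uses the right correlation.
- *MISTIE II shows that stopping at day 180 would mislead.* The differences were 11 points at day 180 and 14 at day 365. The 180-day estimate has a 95% CI of −8.8% to 29.4% (SAP 4.0), so a 3-point gap is within noise.

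It is also fair that the interim is discretionary, and that a stop would not leave day 365 unobserved: about 375 + 60 × 180/182.5 ≈ 434 patients would be enrolled and followed. What is missing is the rule for testing them. An early look may have been intended, since SAP 12.0 was otherwise rewritten, but it gives no reason for day 180.

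**Conclusion.** The concern holds in this form: the stopping rules were not aligned with the 365-day primary. As written, an efficacy stop on 180-day mRS is possible, and the look that exhausts alpha may run with up to about 12% of patients short of day 365 (up to about 16% at the interim). The counts assume steady accrual at the SAP's rate and are upper bounds.

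The effect on type I error is small if both looks test day 365: at most about 0.0264 against 0.025 one-sided, at the lowest information fraction. The more serious part is the unnamed interim endpoint, because it governs an irreversible decision.

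**What to change.** In SAP 12.0:
1. Trigger the final analysis when every randomized patient has completed the 365-day visit, died or been lost to follow-up.
2. State that the interim tests the 365-day estimand with the 11.1 estimator, and that crossing a boundary on 180-day mRS does not reject the 365-day null.
3. Keep the interim spend of 0.0105 if wished, but compute the final boundary from the actual information (correlation) on the 365-day estimate. At the floor of 0.63 this is z of about 2.05, not 2.02.

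Align SAP 2.3.2 with the same wording.

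The cost is SAP text and a final lock about six months later, for visits already in the schedule. Delaying the interim until 375 patients have 365-day data is not required and is a real trade-off: about 375 + 2 × 60 = 495 of 500 would already be enrolled, so the look could hardly shorten recruitment.

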13.0. Secondary Efficacy Outcomes Analyses

13.1. Secondary Efficacy Analysis 1: Dichotomized eGOS UGR-US vs. LS-Death at 365 days

Analyses will follow the methods as described in equations 1, 2, and 3 above (11.2.1–11.2.5). Subordinate analyses will be adjusted for other clinically meaningful variables, in addition to the ones used in the covariate-adaptive randomization.

13.1.1. Additional, Subordinate Efficacy Analysis 1: 365-Day Ordinal eGOS

Clot removal with MIS+rt-PA produces improvements in functional outcome assessed by alternative outcome measures such as the extended Glasgow Outcomes Scale (eGOS). Analyses: Ordinal, linear, logistic, and polytomous data models to examine other levels of the eGOS as part of Secondary Efficacy Analysis 1 will be similar to those presented above.

Minimally Invasive Surgery Plus rt-PA for ICH Evacuation Phase 3

13.2. Secondary Efficacy Analysis 2: All-Cause Mortality Longitudinally from Ictus to 365 Days

Mortality at 365 days post ictus for MIS+rt-PA–treated subjects will be improved as compared to that of medical managed subjects. Comparison of treatment groups will be examined using logistic regression analysis.

Mortality by group will be graphically displayed with Kaplan-Meier curves, and the statistical association between treatment assignment and mortality will be assessed with the log-rank test. Multivariable Cox regression models will then be created to assess for treatment differences in the hazards of survival after adjusting for potential group imbalances in the covariates listed above. Finally, we will account for the effect of the decision to withdraw patient care on treatment differences in mortality.

As a secondary assessment, time to death within the one-year follow-up period will be compared between the MIS+rt-PA and medically managed groups adjusting for appropriate baseline covariates. Provided the model assumptions are met, a proportional hazards regression model may be used for the analysis as described above.

13.2.1. Subordinate, Secondary Efficacy Analysis 2: Predictors of Mortality Analysis

Additionally, survival models will be constructed to examine the mortality, morbidity, and ICU distributions for the MIS+rt-PA and medical management groups. Standard Cox proportional hazard models will initially be examined. These models are commonly written as:

$$h_i(t) = \lambda_0(t) \exp(\gamma X + \phi \cdot TRT)$$

where $\lambda_0(t)$ is a non-parametric baseline hazard function, γ is again a vector of regression coefficients related to the X covariates, and ϕ is the parameter for the treatment effect of EVD plus rt-PA on the hazard of death (mortality). This model may be extended by including time-dependent covariates and non-proportional hazards as deemed necessary through diagnostic checks. Observed mortality will also be compared with predicted mortality based on clinical presentation, overall, and by treatment group. Predicted mortality will be estimated. We will develop a severity model for predicting mortality based on the Tuhrim model.^{2,7,8}

13.3. Secondary Efficacy Analysis 3: Relationship Between Clot Removal as an AUC that Estimates the Time-Weighted Clot Volume from Ictus to EOT as AUC Clot Exposure and Functional Outcome (Proportion 0-3 mRS)

EOT clot volume and/or percent EOT ICH reduction are related to mRS functional outcome regardless of treatment. Based on the experience of the CLEAR III trial, time-weighted average clot volumes will also be considered as a potential predictor of mRS outcome. The null hypothesis is that ICH clot reduction time course (time weighted clot volume, EOT clot volume, and/or percent EOT clot reduction) has no effect on functional outcome regardless of treatment.

In addition, since a "plateau" or "floor" effect of clot resolution over time is likely, subsequent models to statistically test for these fixed effects will consider clot resolution in non-linear terms, such as linear or restricted cubic splines and other non-linear functions. Placement of knots for the splines will be based on the visual inspection of the average ICH trajectory over time. In addition, when using restricted cubic splines, we will consider placing the knots at equally spaced percentiles of the "follow-up time" variable's marginal distribution as recommended by Harrell.⁹ Alternative methods that quantify the time-weighted clot volume will also be considered in this model.⁷

From the final, most parsimonious model, the empirical Bayes estimates of the random slopes will be computed to be used in the next phase. The second-phase analysis will be based on multivariable logistic regression models that include the estimated clot resolution trajectories over time, the covariates listed in equation (1) above, and the dichotomized mRS at 365 days post-stroke as the outcome.

13.4. Secondary Analysis 4: Patient Disposition

13.4.a. Secondary Efficacy Analysis 4a: Home Days Over 365 Days' Time from Ictus

Multivariable linear regression models will be built on this continuous outcome of time to home.

13.4.b. Secondary Efficacy Analysis 4b: Patient Location at 365 Days Post Ictus

Multivariable logistic regression models will be built on the dichotomized outcome of home plus rehabilitation locations versus other locations for patients 365 days post-ictus. Because variations in the more severe levels of mRS (4,5) and eGOS (US, LS, VS) do not fully account for disposition, it will be assessed by adjusting for all covariates. Where discrepant conclusions about severe disability might be drawn from mRS, eGOS, or final location, all three descriptors will be presented for the severe levels.

